5.6 Risk of contamination and clustering in the control arm

Midwives leading the group antenatal sessions will potentially lead multiple different groups of women over the course of the trial. Information on midwifery group leaders is not systematically collected so that this cannot be accounted for in analysis models. Moreover, some of the midwives who have been trained to lead the group pregnancy circles (intervention) will most likely also be leading the one-on-one sessions (standard care) with women in the trial. This potentially contaminates those women in the control group receiving a one-on-one session from such a midwife, as they may unknowingly alter how they run their session. For the purposes of this study the team has not tracked which midwives are leading which sessions, so there is no way of quantifying the effect this may have. But if there is any observable impact, it will be to dilute the treatment effect, i.e. conservative. In other terms, it would be in favour of not rejecting the null hypothesis if the intervention has a positive effect on babies' health. Those risks are accepted in knowledge accordingly.

5.7 Multiple testing

No formal adjustment for multiple testing will be made. However, the number of secondary outcomes will be noted when reporting results.

5.8 Estimand Framework

Inference on the primary and secondary outcomes is complicated by the potential occurrence of intercurrent events. An intercurrent event is defined as an event that happens after randomisation which either affects the measurement, interpretation or existence of an outcome. The 2020 ICH E9 R1 addendum lays out a framework for providing a clear description of the treatment effect to be estimated from a trial (11). The table below describes the treatment effect to be estimated for REACH using the estimand framework.

Estimand framework summary for primary outcome

P	Population	Variable	Summary	Treatment	Detential
			Measure	rreatment	Potential Intercurrent Events*
objective is to demonstrate superiority of Pregnancy Circles over standard individual antenatal care on the health of babies. The primary comparison of having a healthy baby (yes/no) will be made regardless of whether women withdraw from the assigned antenatal care or	Pregnant women registering for antenatal care with NHS maternity services excluding women defined in the exclusion list of section 6 of the trial protocol. All women who during the pandemic were not able to receive the intervention or were only able to receive a low dose of intervention are excluded.	The "healthy baby" composite consists of the following 4 components: 1. Live baby (i.e. no pregnancy loss before or after 24 completed weeks and no neonatal death within 28 days of the birth) 2. Born at term (37 weeks and above) 3. Appropriate weight for gestational age (GROW centile >9.99 & <90.01) 4. Not admitted to a neonatal care unit (which includes Intensive Care Unit, SCBU and High Dependency Unit, but NOT transitional care) A baby is considered a "healthy baby" only if the answer to all above	Marginal Odds ratio and risk difference.	Pregnancy circles groups composed of 8 to 12 women during 8 sessions of 2 hours from week 16 of pregnancy (roughly 1 session every 17.5 days).	Intercurrent Events* Woman stops intervention at any point for any reason Develop complications and become higher risk — woman ask to have 1-2-1 Change of service because of pandemic or relocation Rates of induction going up Woman switches circle before attending first antenatal care session Woman switches circle after attending first antenatal care session

^{*}The treatment policy strategy (regardless of intercurrent event) will be used for all intercurrent events except for "Woman switches circle before attending first antenatal care session" where we will use the as-treated strategy (data will be analysed considering the circle women actually attended from the beginning).

PCTU_TEM_ST_02 Statistical Analysis Plan template V 3.0

5.9 Analysis of primary, secondary and additional outcomes

The following table shows the variable type of outcomes in this study:

		•
	Outcomes:	
Binary	Continuous	Categorical
-healthy baby composite	-attendance at antenatal care	-continuity of care
-spontaneous vaginal delivery	-women's empowerment	-Caesarean delivery
-breast feeding initiation	-social support	-place of birth
-breastfeeding continuation	-self efficacy	- additional measures of
-postnatal depression	-prenatal stress	satisfaction
-live baby	-health literacy	- choice and involvement in
-born at term	-mental wellbeing	care
-appropriate weight for	-postnatal symptoms	- preparedness for labour
gestational age	-satisfaction with care	- confidence in caring for baby
-not admitted to a neonatal	-Infant birth weight in grams	- immunisation
care unit		

Main analysis model (binary outcome)

The primary outcome data for the 'Healthy Baby' composite will be extracted via a postpartum maternity records audit and be analysed using a nested multilevel logistic mixed effects model with two random intercepts estimating a cluster and site-specific effects in both arms (1). Although site is a stratification factor, it has been included as a random effect due to the high number of sites included. In the intervention arm, within Pregnancy Circle cluster correlation will be accounted for and in the control arm each participant will be modelled as a cluster of size 1. The other stratification factor used in this trial is the ability to speak English and will be included as a fixed effect covariate. The resulting model will produce an odds ratio for the odds of giving birth to a 'healthy baby' in the intervention versus the control arm. The outcome will be assessed at the participant's level (mother) following this rule: if a mother has multiple births for the same delivery (e.g. twins), the 'Healthy Baby' composite will be equal to 'yes' only if all babies are healthy. Otherwise, Healthy baby will be equal to 'no'.

Specifically, let y be the binary outcome, i is the individual participant indicator (mother), j is the pregnancy circle indicator, t is the intervention indicator (0 = control, 1 = intervention), θ is the intervention effect, θ_0 is an intercept term, I is the site indicator, and θ_{ki} represents further covariates (ability to speak English in this instance). Then,

$$Logit[Pr(y_{iil}=1)] = \beta_0 + \theta t_i + \beta_{ki} + v_l + u_i$$

where $u_j \sim N(0, \sigma^2_u)$ is a random-effects term representing between-cluster (pregnancy circle) variation in the clustered intervention arm and $v_l \sim N(0, \sigma^2_w)$ is the random effect representing between-site variation.

Accounting for non-collapsibility

Odds ratios present the characteristic of non-collapsibility when adjusted on covariates. To deal with that phenomenon, the g-computation estimator will be used for covariate adjustment following the 6 steps described below as described in the FDA's guidance for covariate adjustment [13]:

- (1) Fit a logistic model with maximum likelihood that regresses the outcome on allocation assignments and prespecified baseline covariates. The model will include an intercept term.
- (2) For each subject, regardless of allocation assignment, compute the model-based prediction of the probability of response under pregnancy circle group using the subject's specific baseline covariates.
- (3) Estimate the average response under pregnancy circle group by averaging (across all subjects in the trial) the probabilities estimated in Step 2.
- (4) For each subject, regardless of allocation assignment, compute the model-based prediction of the probability of response under usual care using the subject's specific baseline covariates.
- (5) Estimate the average response under usual care by averaging (across all subjects in the trial) the probabilities estimated in Step 4.

The estimates of average responses rates in the two allocation groups from Steps 3 and 5 will be used to estimate an unconditional intervention effect. Risk differences, and odds ratios will both be presented for primary and secondary outcomes. Confidence intervals will then be estimated using bootstrap.

Any of the secondary or additional outcomes which provide binary responses (spontaneous vaginal delivery, infant low birthweight, etc.) will be analysed using the same nested multilevel logistic mixed effects model.

Analysis of continuous outcomes

Secondary and additional outcomes providing continuous responses, such as a total score on any of the scales being used, will be analysed by assessing difference of means between intervention and control groups. This will be analysed using a partially nested mixed-effects model with heteroskedastic error terms with the Satterthwaite approximation for degrees of freedom to avoid upward bias of the type-I error rate (2). The English level will again be included as covariate in these models. The resulting model will estimate a difference of means between the intervention and control arms of the study. Specifically, let y be the continuous outcome, i is the mother participant indicator, j is the pregnancy indicator, t is the intervention indicator (0 = usual care, 1 = pregnancy circle), θ is the intervention effect, θ_0 is an intercept term, and θ_k represents fixed effects for English level. Then,

$$y_{ij} = \beta_0 + \theta t_{ij} + \beta_k + u_i t_{ij} + r_{ii} (1 - t_{ij}) + \epsilon_{ij} t_{ij} + v_1$$

where $u_j \sim N(0, \sigma^2_u)$ is a random-effects term representing between-cluster (pregnancy circle) variation in the clustered intervention arm, $r_{ij} \sim N(0, \sigma^2_r)$ represents individual-level variation in the

non-clustered control arm, $\epsilon_{ij} \sim N(0, \sigma^2_{\epsilon})$ represents individual-level variation in the clustered intervention arm and $v_i \sim N(0, \sigma^2_w)$ is the random effect representing between-site variation.

Analysis of categorical outcomes

For categorical outcomes, proportions by intervention group and test of between group difference without covariate adjustment will be presented.

Strategy for analysis of primary outcome if model fails to converge

In case the analysis of the primary outcome described above fails to converge, the following sequential strategy will be employed (starting at 1).

	Change from previous strategy
1	Try an alternative estimation algorithm, such as the
	QR decomposition in meqrlogit, rather than Stata's
	default melogit function.
2	Change the number of integration (quadrature)
	points for all levels using intpoints() command
3	Try an alternative integration method other than
	mean-variance adaptive Gauss-Hermite
	quadrature like Laplace for example.
4	Remove covariate English speaking level from the
	model.
5	Analysis using model, not assounting for clustering
5	Analyse using model, not accounting for clustering
	within intervention groups.
6	In addition to removing random effect in (5)
	remove random effect for site

For any of the binary secondary outcomes that fail to converge, the process above will be repeated for the multilevel logistic mixed effects regression models.

Strategy for analysis of continuous outcomes if model fails to converge

In case the analysis of any secondary outcome fails to converge, the following strategy will be employed.

	Change from previous strategy
1	Try an alternative optimisation algorithm, such as
	the Newton Raphson algorithm, rather than Stata's
	default for xtmixed.
2	Try an alternative estimation method other than
	REML such as MLE or quasi likelihood based
	methods.
3	Fit an alternative clustering model with participants
	in the control arm treated as clusters of size 1.
4	Remove fixed effect covariate from the model.

5	Analyse using model, not accounting for clustering by intervention group.
6	Analyse using fixed effects model removing random effect for site in addition to random effect I (5)

Furthermore, if any issues arise for categorical additional outcomes, the outcome categories will be recoded as described in the table below.

Categorical outcomes breakdown				
Outcome	Categories	Modified categories for		
		convergence issues		
Continuity of care	1-2 midwives	1-2 midwives		
	3 midwives	3+ midwives		
	4+ midwives			
Caesarean delivery	Planned	Any Caesarean		
	Emergency	None		
	None			
Place of birth	Hospital obstetric unit	Hospital (anywhere)		
	Hospital alongside midwifery	Freestanding midwifery unit		
	unit	Other		
	Freestanding midwifery unit			
	Home			
	Other			

If problems with other categorical outcomes names in 3.4 occur a similar collapsing strategy will be employed.

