4.1 Sample size

4.1.1 Sample size calculation (pre covid)

For the primary outcome ("Healthy baby"), in order to detect a difference in babies born "healthy" of 8% between the control and intervention arm, with 90% power and a 5% significance level, we would require at least 866 women per arm (i.e. 1732 total). This calculation also assumed an outcome proportion of 69% in the control arm, accounts for clustering within the intervention arm with an intra-cluster correlation (ICC) of 0.05 (in the intervention arm), mean group sizes of 8 with cluster size variability assuming Poisson distribution and assumes 10% drop-out in both arms. This sample size provides 84.8% power to detect a difference between arms of 7.3% in our, former primary outcome, spontaneous vaginal birth. Thus, a sample size 1732 is sufficiently powered to detect changes in both the primary outcome and SVD (now a secondary outcome).

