5.5 General analysis principles

The analysis of primary, secondary, and, where possible, additional outcomes will be adjusted for the stratification factors which were used during randomisation, centre, and ability to speak English, only. All main analyses will be performed on a complete case basis (ignoring missing data) for the outcomes in question. A missing category will be created for the only covariate in the models "ability to speak English". The significance for statistical tests (alpha) will be 5%, all confidence intervals will be presented at the 95% level and all p-values will be two-sided. As the intervention arm includes group pregnancy circles, clustering will be accounted for in the intervention arm using pregnancy

circles as the units of clustering, while participants in the control arm will be modelled as a cluster size of one [1].

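### Circle clustering is not carried into the g-computation and bootstrap that yield the primary odds ratio and risk difference; if women are resampled singly, the 95% interval is about 8–9% too narrow

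*SAP*

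**What the plan says.** Section 5.5 sets a general rule: "clustering will be accounted for in the intervention arm using pregnancy" circles as the clustering unit, with each control woman as a cluster of one. The main binary model in section 5.9 follows it, with random intercepts for circle and site.

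The estimand table in section 5.8 names a marginal odds ratio and risk difference as the summary measures. Section 5.9 derives these under its non-collapsibility heading. Step (1) reads "Fit a logistic model with maximum likelihood that regresses the outcome on allocation assignments and prespecified baseline covariates", and the predictions that follow use baseline covariates only. For the interval the text says "Confidence intervals will then be estimated using bootstrap". It gives no resampling unit, number of replicates or interval type. It announces six steps and numbers five.

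Two other places in section 5.9 bear on the same point:
- Step 5 of the binary non-convergence ladder is "Analyse using model, not accounting for clustering" within intervention groups, and step 6 also removes site. The continuous ladder does the same at its steps 5 and 6.
- For categorical outcomes, proportions and a "test of between group difference without covariate adjustment will be presented". The test is not named and clustering is not mentioned.

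Dummy Table 2 (section 8.4) puts the odds ratio, risk difference, one p-value and the circle ICC in a single row.

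**The concern.** The circle effect sits in the mixed model, whose odds ratio is conditional on the random effects and so is not the stated estimand. The quantities that are the estimand come from a procedure in which circle does not appear.

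Nor can the mixed model be put into the steps without further instruction. Predicting a control woman's outcome under group care needs a rule for her circle effect: set it to zero, or integrate over its distribution. The SAP gives neither.

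What is at stake is the nominal coverage of the primary interval. The source of the p-value in Table 2 is also unstated. If it comes from the mixed model while the interval comes from a bootstrap that ignores circles, the two may disagree in one row. Section 5.9 applies the same reporting to binary secondary outcomes.

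**Working it through.** **Inputs.** From section 4.1.1: "with 90% power and a 5% significance level"; the calculation "assumed an outcome proportion of 69% in the control arm"; a difference of 8 percentage points, so 77% in the intervention arm; ICC 0.05 in the intervention arm only; mean circle size 8, Poisson; 10% drop-out. From section 5.5: "all p-values will be two-sided". From section 4.2: 1:1 allocation.

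**Design effect.** DE = 1 + [(1 + CV²)m − 1] × ICC. With Poisson sizes CV² = 1/m, so DE = 1 + m × ICC = 1 + 8 × 0.05 = 1.40 in the intervention arm, and 1 in the control arm.

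**Reproducing the sample size.** Two proportions, 0.69 v 0.77, two-sided 5%, 90% power: 646 per arm. The average design effect is (1 + 1.40)/2 = 1.20. Then 646 × 1.20 = 775, and 775/0.9 gives 862, against the SAP's 866. Applying the design effect to the intervention-arm variance gives 855 (pooled null variance) or 843 (unpooled). All are within 3% of 866, so the sample size does allow for clustering.

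**If the interval ignores circles.** With arm variances v₀ and v₁, the ratio of the naive to the correct standard error is √[(v₀ + v₁)/(v₀ + DE·v₁)].
- No effect (v₀ = v₁): √(2/2.40) = 0.913. Type I error = 2[1 − Φ(1.96 × 0.913)] = 7.4%.
- 69% v 77%: v₀ = 0.69 × 0.31 = 0.2139 and v₁ = 0.77 × 0.23 = 0.1771. The ratio is √(0.3910/0.4618) = 0.920. Coverage = 2Φ(1.96 × 0.920) − 1 = 92.9%.

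**Simulation.** 2,000 partially nested trials per scenario, beta-binomial circles with ICC 0.05, 779 women per arm, 400 bootstrap draws. There were no covariates, so g-computation reduces to the simple risk difference.

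| True rates | Coverage, women resampled | Coverage, circles resampled | Width ratio |
|---|---|---|---|
| 69% v 69% | 91.7% | 93.9% | 0.918 |
| 69% v 77% | 91.7% | 94.1% | 0.924 |

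**Sensitivity of type I error when circles are ignored** (ICCs other than 0.05 are assumptions).

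| ICC | Mean size | DE | Type I error |
|---|---|---|---|
| 0.01 | 8 | 1.08 | 5.5% |
| 0.02 | 8 | 1.16 | 5.9% |
| 0.05 | 8 | 1.40 | 7.4% |
| 0.05 | 12 | 1.60 | 8.6% |
| 0.10 | 8 | 1.80 | 9.8% |

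**Should circles be resampled within site?** Section 8.3 gives 45 + 33 = 78 circles whose women stay in the primary analysis. The 566 later recruits would add about 566/2/8 ≈ 35, so about 113 in all. Over the 18 site codes in Table 7 that is about 6 per site (an assumption). Resampling 6 units within a stratum shrinks the bootstrap variance by the factor 5/6. The total becomes 1 + 1.40 × 5/6 = 2.167 instead of 2.40, and √(2.167/2.40) = 0.95. The standard error is then about 5% too small, which gives back over half of the correction.

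**The case against.** The strongest reply is that the SAP nowhere says women are resampled singly. The rule in section 5.5 has no exception for the bootstrap, so circle resampling is the reading consistent with it. A circle-level bootstrap would also be adequate around a plain logistic point estimate, as the simulation shows. Step (1) follows the cited regulatory guidance and comes directly after the mixed model, so it may be shorthand for that model; site, at least, could count as a prespecified covariate. All of this stands. A reader might infer that the primary interval is certainly too narrow. The text does not support that: it leaves the choice open and does not carry the clustering rule into the step where it is needed.

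A reader might also infer that the fallback ladders discard clustering readily. They do so only after four earlier steps. One common cause of non-convergence is a circle variance near zero, where little would be lost.

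For the categorical outcomes a reader might infer a large error inflation, for example for the number of midwives seen. That needs ICCs well above 0.05, which the SAP does not give. These are additional outcomes, which section 3.4 says serve mainly for hypothesis generation, and Table 4 reports p-values without intervals.

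Finally, an interval and a p-value from two methods can differ even when both respect clustering, so that disagreement is not due to clustering alone.

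**Conclusion.** The point holds as a gap in specification with a conditional consequence. Clustering by circle is required in section 5.5 and modelled in section 5.9, but it is not carried into the procedure that produces the primary marginal odds ratio and risk difference.

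The size given above (7.4% type I error, 92–93% coverage, an interval 8–9% too narrow) rests on two conditions: that women are resampled singly, and that the planning ICC and circle size are right. At a small ICC the effect is slight. The trial recruited for a design effect of 1.40, so the primary interval should reflect it without relying on the analyst's reading.

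The explicit loss of clustering at ladder steps 5 and 6 is a secondary matter, avoidable at no cost. The categorical tests are a lesser point: their p-values may be too small, by an amount the SAP's figures cannot establish.

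**What to change.** - **Model.** State that g-computation uses the fitted mixed model with predictions integrated over the random effects. Alternatively, state that it uses a plain logistic model with a cluster-aware variance.
- **Bootstrap.** Resample whole circles in the intervention arm and single women in the control arm, stratified by arm. Do not stratify by site unless a small-strata correction is applied. Give the number of replicates and the interval type, and correct the count of steps.
- **P-value.** Take it from the same procedure as the interval, and say so under Table 2.
- **Ladders.** Replace steps 5 and 6 in both with logistic or linear regression using cluster-robust standard errors by circle, with controls as singletons.
- **Categorical outcomes (lesser point).** Name a cluster-adjusted test, such as a Rao–Scott chi-square.

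The cost is SAP wording and computing time. Compared with resampling women singly, intervals become about 9% wider at the planning ICC (1/0.920 = 1.087 to 1/0.913 = 1.095), which the sample size already allows for.

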4.2 Randomisation procedure

Women will be randomised to receive current standard mid-wife led antenatal care (control) or entered in the pregnancy circles groups (intervention) with a 1:1 allocation ratio. If recruited in person, each woman will be told her allocation status face-to-face straight away. Each pregnancy circle will consist of 8-12 pregnant women who have estimated delivery dates within the same approximate one-month period. Women will be randomised using randomly permuted blocks of 4, 6 or 8 and randomisation will be stratified by the location (site) of the Pregnancy Circle and on a woman's ability to speak English a) well/very well or b) not well/not at all.

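### SAP 5.9 tests every categorical outcome without the randomisation strata and without circle clustering, so these p-values can be miscalibrated in either direction

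*SAP*

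**What the plan says.** - **Design.** SAP 4.2: "randomisation will be stratified by the location (site) of the Pregnancy Circle and on a woman's ability to speak English", "with a 1:1 allocation ratio".
- **General rule on strata.** SAP 5.5: "The analysis of primary, secondary, and, where possible, additional outcomes will be adjusted for the stratification factors which were used during randomisation".
- **General rule on clustering.** SAP 5.5 says "clustering will be accounted for in the intervention arm using pregnancy" circles as the unit, with controls as clusters of size one. This sentence has no qualifier.
- **Binary and continuous outcomes.** The models in 5.9 carry site as a random effect, English level as a fixed effect and a circle random effect. This includes the additional outcomes of these types.
- **Categorical outcomes.** SAP 5.9: "For categorical outcomes, proportions by intervention group and test of between group difference without covariate adjustment will be presented". No test is named, no reason is given for dropping the strata, and no clustering method is mentioned.
- **Recoding.** Later in 5.9: "if any issues arise for categorical additional outcomes, the outcome categories will be recoded as described in the table below". The column with the collapsed categories is headed as being for convergence issues.
- **Reporting.** Dummy Table 4 has counts, percentages and a p-value. Tables 2 and 3 also have an effect estimate, a confidence interval and an ICC.
- **Status.** All categorical outcomes are additional outcomes under 3.4, meant mainly for hypothesis generation.

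**The concern.** Stratified randomisation removes between-site differences from the arm comparison. A test that ignores site still counts that variation as error, so its standard error is too large and it rejects too seldom. Several of these items plausibly vary by site: place of birth depends on which units a Trust runs, and the number of midwives seen depends on local organisation.

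The same plain test treats women in one circle as independent. That makes the standard error too small and works in the opposite direction.

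The p-value is the only inferential result that Table 4 gives for caesarean type, place of birth, continuity, choice and preparedness. If its calibration depends on which of the two omissions dominates for a given item, a reader cannot interpret it. The recoding table adds doubt about which analysis is meant, because a simple test of proportions has no convergence step.

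**Working it through.** **1. The plan's own clustering inputs.** SAP 4.1.1 gives 69% v 77%, 90% power, two-sided 5%, ICC 0.05 in the intervention arm, mean group size 8 with Poisson variability, and 10% drop-out.

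- Design effect in the intervention arm: DE = 1 + [(1 + 1/8) × 8 − 1] × 0.05 = 1.40.
- n per arm = (1.960 + 1.282)² × [0.69 × 0.31 + 1.40 × 0.77 × 0.23] / 0.08² = 758, and 758/0.90 = 842. With pooled variance under the null: 769, and 769/0.90 = 855.
- The SAP states 866, within 3% of both. The figure is reproduced, so DE = 1.40 is the clustering the plan itself allows for.

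**2. Strata omitted, no circle effect.** Let R² be the share of outcome variance between sites. The SAP gives no value, so a range is shown. With 1:1 allocation within sites, the true variance of the arm difference is (1 − R²)V, while the unadjusted test uses V.

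- Size = 2Φ(−1.96/√(1 − R²)).
- Take an effect with nominal 70% power, δ = 1.960 + 0.524. Unadjusted power = Φ(0.524/√(1 − R²)). Stratified power = Φ(δ/√(1 − R²) − 1.96).

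**3. Strata and circles both omitted.** Circles inflate one arm only, so the average inflation is (1 + 1.40)/2 = 1.20 and the true variance is (1.20 − R²)V.

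- Size of the planned test = 2Φ(−1.96/√(1.20 − R²)).
- Size if only strata are added = 2Φ(−1.96/√[(1.20 − R²)/(1 − R²)]).

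| R² | Size, strata omitted, no circle effect | Power, unadjusted → stratified, no circle effect | Size, strata and circles omitted | Size, strata added, circles omitted |
|---|---|---|---|---|
| 0% | 5.0% | 70.0 → 70.0% | 7.4% | 7.4% |
| 5% | 4.4% | 70.5 → 72.2% | 6.8% | 7.5% |
| 10% | 3.9% | 71.0 → 74.5% | 6.2% | 7.6% |
| 15% | 3.4% | 71.5 → 76.9% | 5.6% | 7.8% |
| 20% | 2.8% | 72.1 → 79.3% | 5.0% | 8.0% |
| 25% | 2.4% | 72.8 → 81.8% | 4.4% | 8.2% |

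**4. Simulation check.** A three-category outcome was simulated with 14 sites, 8 circles of exactly 8 women per site and 896 women per arm (5000 null runs, 4000 power runs). Correlations were set on an underlying continuous scale, which weakens them once the scale is cut into categories. The results are therefore milder than the formula.

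- Circle ICC 0.05, unadjusted chi-squared: type I error 6.1%, 6.7%, 5.8% and 5.0% at site ICC 0, 0.02, 0.05 and 0.15. The Monte Carlo standard error is √(0.05 × 0.95/5000) = 0.3 points.
- Circle ICC 0.05, site-stratified Cochran-Mantel-Haenszel (CMH) test: 6.1% to 6.9% over the same range.
- No circle correlation, power unadjusted v stratified: 65.4 v 66.0%, 65.9 v 67.3% and 67.5 v 72.3% at site ICC 0.02, 0.05 and 0.15.

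**The case against.** **Section 5.5 is not breached on the strata.** A reader might infer a flat contradiction. The text does not support that: for these outcomes the rule reads "and, where possible, additional outcomes will be adjusted for the stratification factors which were used during randomisation", and a specific sentence in 5.9 may use that exception. What stands is that the exception goes unexplained although adjustment can be done with data already held. The clustering rule in 5.5 has no such exception.

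**The tests are not simply conservative.** A reader might infer this from the missing strata. It holds only if circle correlation is zero. At the SAP's own ICC and mean circle size, the net error is above 5% unless sites differ strongly.

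**5.9 does not rule out handling clustering.** It says only that covariates are left out, so 5.5 could still be read as binding. But no method is named and Table 4 has no ICC column, so an analyst following 5.9 would run a plain test.

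**Collapsing categories also helps a contingency test with sparse cells.** That is fair, and the trigger is worded loosely. The column heading still refers to convergence, which only a fitted model can fail.

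**Adjustment may be hard.** Where a Trust has no unit of a given type, site terms meet empty cells and possible separation. This is a real cost of the remedy, but 5.9 does not offer it as its reason.

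**The stakes are small.** Table 4 also shows proportions by arm, and no primary or secondary result depends on these tests. This limits the importance but does not make the p-values valid.

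**Conclusion.** The point holds in this form: 5.9 drops the randomisation strata for all categorical outcomes without a reason, makes no provision for circle clustering, and includes a recoding table that presupposes a model it does not specify.

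The power lost by omitting strata is about 1 to 2 points at R² of 5% or less, and about 5 points at 15%. With circle clustering also ignored, type I error is about 6% to 7% for most items. By the formula it reaches 5% or below only at R² of about 20% or more; in the simulation it was already 5.0% at an underlying site ICC of 0.15.

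This rests on two assumptions: the range for R², and that the primary outcome's ICC of 0.05 and mean circle size of 8 apply to these items. With a smaller circle ICC, the net error moves back towards the conservative side.

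Importance is low to moderate. The outcomes are hypothesis-generating, and the documents do not support any inference that the primary or secondary conclusions are affected.

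**What to change.** Replace the categorical sentence in 5.9 with wording such as:

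*Categorical outcomes will be compared between arms by ordinal logistic regression (ordered categories) or multinomial logistic regression (unordered categories), including site and English ability. Circle clustering in the intervention arm will be accounted for by a circle random effect or a circle-robust variance, with each control participant as a cluster of size 1. Where cells are sparse, categories will be collapsed as tabulated.*

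Add the adjusted estimate with its 95% CI to Table 4. For ordered items, also say how don't-know answers are handled.

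A strata-only CMH test should not be the fallback unless its variance is corrected for circle clustering. On its own it leaves type I error at about 7% to 8% by the formula (6.1% to 6.9% in the simulation), and it removes the accidental offset that between-site variation gives the plain test.

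The cost is SAP wording and a few lines of Stata, with no new data and no further participants. The downside is sparse cells or separation in some sites, for which the existing collapsing table now has a clear use. If the team prefers not to model these items, the alternative is to call the comparisons descriptive and remove the p-value column.
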